2.3 Risk/Benefit Assessment

2.3.1 Known Potential Risks

SLV213

Cathepsin inhibitors have been safely used in the clinic (Drake, Clarke et al. 2017; Fuchs, Meta et al. 2020).

Preclinical:

SLV213 is the oral formulation of the drug substance, K777. All preclinical development was conducted with K777 (K11777). The K777 toxicology program included single-dose and repeat-dose oral dose toxicity studies in rats and dogs. Pivotal studies included a 14-day GLP toxicity study in rats, a 28-day GLP toxicity study in dogs as well as standard GLP *in vitro* tests for genotoxicity. Non-GLP studies were also conducted in cynomolgus and rhesus monkeys. In general, K777 was well tolerated in all species after oral administration. The liver was identified as the target organ of toxicity. Reversible increases in transaminases (e.g., aspartate aminotransferase [AST], alanine aminotransferase [ALT]) were reported in all species at high doses. In the GLP 14-day rat toxicity study, the highest dose administered (150 mg/kg/day) produced mild effects on liver enzymes (2-fold elevation) that were not confirmed by histopathologic evaluation of the liver. In the 28-day GLP dog toxicity study, modest reversible elevations in serum transaminases were also observed. In addition, reversible microscopic changes were detected in the brain (100 mg/kg dose; females only) and in lymphoid tissues. These reversible changes were considered non-adverse due to lack of histopathologic, clinicopathologic, and clinical evidence suggestive of an organ or organismal functional impairment.

Modest depressions in food consumption and weight gain were also observed in several studies, but effects were reversible and not considered adverse. Emesis was frequently reported in the dog

at oral K777 doses ~100 mg/kg and was also reported after intravenous (IV) dosing in a recent dog safety pharmacology study. Changes in hematological parameters were not typically observed or not considered of toxicological significance. *In vitro* and *in vivo* GLP studies did not demonstrate genotoxic effects of K777.

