9.3.6 Safety Analyses

AEs will be presented in listings and TEAEs will be summarized. Individual results of laboratory tests, VS, and ECGs will be listed and baseline, post dose, and changes from baseline to post dose laboratory, VS, and ECG data will be summarized.

AEs, including abnormal laboratory values, will be graded according to the protocol Toxicity Tables in [Appendix A](#). PE findings will be presented in data listings.

All AEs occurring after study drug dosing will be summarized using frequency counts and percentages. The following summaries will be presented for TEAEs and SAEs:

- Overall (i.e., regardless of severity or relationship to treatment).
- By severity grade (mild, moderate, or severe).
- By relationship to study drug.
- By MedDRA level hierarchy (system organ class [SOC], higher level group term [HLGT] and preferred term [PT]).

Unless otherwise specified, at each level of subject summarization in reporting the incidence of TEAEs, a subject will be counted once if the subject reported one or more TEAEs. If more than one occurrence of a TEAE is reported, the TEAE of the worst severity or the worst-case relationship assessment will be summarized.

Additional Safety Analyses:

Descriptive summary statistics (mean, standard deviation [SD], median, minimum, and maximum) for all clinical laboratory data, 12-lead standard ECG parameters, and VS at admission and each applicable post-dosing visit, including changes from baseline values, will be calculated and presented by treatment cohort. Baseline values will be the last values recorded before initiating administration of study drug. For change-from-baseline summaries, participants with an undefined change from baseline, due to missing data, will be excluded. Clinical significance of abnormalities,

as assessed by the study PI or authorized study clinicians, will be indicated. The number and percentage of participants who meet toxicity criteria for clinical laboratory, VS and 12-lead ECG investigations will be listed and tabulated by treatment cohort.

Tolerability Assessment:

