## 9. SAFETY EVALUATION

All safety analyses will be performed using the Safety Population and will be presented by Treatment Group. TEAEs will be presented in listings and summarized. Individual results of laboratory tests, VS, and ECGs will be listed and baseline, post dose, and changes from baseline to post dose laboratory, VS, and ECG data will be summarized.

In general, TEAEs, including abnormal laboratory values, will be graded according to the FDA Guidance: Toxicity Grading Scale for Healthy Adult and Adolescent Volunteers Enrolled in Preventive Vaccine Clinical Trials (<https://www.fda.gov/media/73679/download>). Grading scales are provided for AEs (**Table 6**), supine vital signs (**Table 7**), clinical laboratory results (**Table 8**), and ECG results (**Table 9**). Abnormal PE findings will be presented in data listings (**Listing 18**).

Clinical laboratory tests and VS at Screening Visit and Check-in (Day -1) should be within site normal reference range with exceptions as allowed per **Section 4.3.1**, inclusion criterion #4 and outlined in the Manual of Procedures (MOP). Grade 1 measurements acceptable at baseline will only be considered a TEAE post-baseline if condition worsened.

All TEAEs will be summarized using frequency counts and percentages. The following summaries will be presented for TEAEs and SAEs:

- Overall (i.e., regardless of severity or relationship to treatment).
- By severity grade (mild, moderate, severe, or life-threatening).
- By relationship to study drug.
- By MedDRA level hierarchy (system organ class [SOC], higher level group term [HLGT], and preferred term [PT]).

Unless otherwise specified, at each level of participant summarization in reporting the incidence of TEAEs, a participant will be counted once if the participant reported one or more TEAEs. If more than one occurrence of a TEAE is reported, the TEAE of the worst severity or the worst-case relationship assessment will be summarized.

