Laboratory results will be summarized for baseline, Day 2, Day 4, Day 6, and Day 8 in tables and figures:

- Number and percentage of participants with none, mild, moderate, severe, or life-threatening laboratory results both low (decrease) and high (increase) by parameter, time point, and treatment group for CHEM ([Table 33](#)), HEM ([Table 34](#)), COAG ([Table 35](#)), and UA ([Table 36](#)).

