## 9.9. Other Safety Measures

### 9.9.1. 12-Lead Standard Electrocardiogram

Unscheduled ECG measurements will be included in listings but will be excluded from tabular and graphical summaries by time point, except when calculating the maximum severity post baseline. Baseline is defined in [Section 3.1](#). Individual interval measurements and overall interpretations will be presented in [Listing 19](#) and [Listing 20](#), respectively.

---

The sort order for ECG interval measurements will be as follows: PR Interval, QRS Interval, QT Interval, QTcF Interval, RR Interval, and Ventricular Rate.

12-lead standard ECG results will be summarized in tables and figures:

- Summary of 12-lead standard ECG change in overall interpretation from baseline will be shown by treatment group and time point (**Table 38**).
- Number and percentage of participants with mild, moderate, severe, or life-threatening ECG results by parameter, time point, and treatment group (**Table 39**).

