### Changes from Protocol v4.0:

The study did not continue enrollment after Cohort 1 (See [Section 6.2](#)). This SAP provides shells for an abbreviated CSR that will assess 400 mg SLV213 and placebo treatment groups from Cohort 1 only.

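### Protocol 9.3.6 and SAP 9 promise summaries of laboratory, ECG and vital-sign change from baseline, but no SAP section or shell delivers them and SAP 15 does not declare the omission

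*SAP*

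**What the plan says.** Protocol 9.3.6 commits to "Descriptive summary statistics (mean, standard deviation [SD], median, minimum, and maximum) for all clinical laboratory data, 12-lead standard ECG parameters, and VS", both on admission and at each applicable post-dose visit, with changes from baseline, by treatment cohort. SAP 9 makes two separate promises: individual results are listed, and "baseline, post dose, and changes from baseline to post dose laboratory, VS, and ECG data will be summarized". SAP 6.1 adds a general rule that continuous variables get n, mean, SD, median, maximum and minimum.

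The sections that specify outputs are narrower. SAP 9.6 gives one laboratory summary, shown by treatment group in Tables 33-36: "Number and percentage of participants with none, mild, moderate, severe, or life-threatening laboratory results both low (decrease) and high (increase) by parameter, time point". SAP 9.7 gives the same kind of count for supine vital signs (Table 37). SAP 9.9.1 gives a shift in overall ECG interpretation (Table 38) and "Number and percentage of participants with mild, moderate, severe, or life-threatening ECG results by parameter, time point, and treatment group" (Table 39).

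SAP 15 lists a single change from Protocol v4.0: "The study did not continue enrollment after Cohort 1", so the shells serve an abbreviated report on the Cohort 1 groups. It says nothing about dropping numeric safety summaries.

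**The concern.** A grade count registers a participant only when a value crosses a limit. A shift of a whole group that stops short of the limit leaves no trace in such a table, and the comparison of SLV213 with placebo is not made for it. In a cohort planned as 8 on SLV213 and 4 on placebo, grade counts are coarse, and the mean and range of the change carry much of the information.

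The liver is where this matters most. Protocol 2.3.1 names it as the target organ of toxicity and reports reversible transaminase rises at high doses in all species, including a two-fold rise at the top dose of the 14-day rat study. Inclusion criterion 4 requires ALT and AST within the normal range at entry, so participants should start below the grading limits.

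**Working it through.** The plan states no figure to reproduce. The check has two parts: match each output to the promise, then apply the SAP's own grade limits.

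**1. Outputs against the promise**

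| Output | Content | Mean, SD, median or range of value or change by group? |
|---|---|---|
| Tables 29-32 | Participant listing of laboratory results outside the normal range, including ungraded ones | No |
| Tables 33-36 | Counts by toxicity grade, laboratory | No |
| Table 37 | Counts by toxicity grade, supine vital signs | No |
| Table 38 | Shift in overall ECG interpretation (normal/abnormal) | No |
| Table 39 | Counts by toxicity grade, PR and QTcF | No |
| Figures 1-10 | Design, disposition, PK, related adverse events | No, although SAP 9.6 and 9.9.1 mention figures |
| Listings 13-15, 19 | Individual laboratory and ECG values with change from baseline | By participant only |
| Listings 16, 17 | Urinalysis and vital signs, without a numeric change column | No |

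Shells with these statistics do exist for demographics (Table 13) and PK (Tables 15-21).

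Some collected parameters get no numeric group summary at all. Chloride, eGFR and direct bilirubin are absent from the Table 33 parameter order, red cells from Table 34 and INR from Table 35. QRS, QT, RR and ventricular rate are absent from Table 39. INR is part of the liver halting rule in protocol 7.1.1.

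**2. ALT**

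SAP Table 8 starts ALT Grade 1 at 44 U/L (women) and 60 U/L (men). Neither limit refers to the participant's baseline.

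- Women: highest ungraded whole value is 44 − 1 = 43; 43/2 = 21.5, so the largest baseline is 21, and 2 × 21 = 42 < 44.
- Men: highest ungraded whole value is 60 − 1 = 59; 59/2 = 29.5, so the largest baseline is 29, and 2 × 29 = 58 < 60.

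One step higher, 22 becomes 44 and 30 becomes 60, both Grade 1.

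Illustration with assumed values: 4 women at 21 U/L and 4 men at 29 U/L on SLV213, all doubling.

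- Baseline mean: (4 × 21 + 4 × 29)/8 = 200/8 = 25 U/L.
- Post-dose mean: 50 U/L, a mean change of +25 U/L.
- Table 33: all eight are *None*. Its display rule then shows only the *None* row for that group, exactly as it would for a group with no change.

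**3. QTcF and blood pressure**

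SAP Table 9 starts QTcF Grade 1 at 451 msec (men) and 471 msec (women), and grades a rise from 30 msec upward. A man going from 421 to 450 msec, or a woman from 441 to 470 msec, has risen by 29 msec and is ungraded. In Table 7, systolic pressure from 90 to 140 mmHg carries no grade, a span of 140 − 90 = 50 mmHg.

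**4. Where change already enters the grades**

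Hemoglobin decrease is graded on change from baseline (Table 8), and so is QTcF prolongation from 30 msec upward (Table 9). ALT has no such row.

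**The case against.** The strongest reply is that the analysis has not been withdrawn. SAP 6.1 and SAP 9 still state it, and SAP 1 calls the shells samples. A reader might infer that the SAP has replaced the promised analysis with grade counts alone. The documents do not support that: the commitment remains in the text, Table 38 is not a grade count, and hemoglobin and QTcF have change-based grades. But SAP 1 also says the document covers every planned analysis, and no operative section or shell implements this one.

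Second, nothing is hidden at participant level. Tables 29-32 list every out-of-range laboratory result, and Listing 13 gives each ALT value with its change, sorted by treatment group. With 12 planned participants plus the 4 replacements described in SAP 6.2, about 16 in all, a reader could find an ALT doubling by eye. This stands as a limit on the harm. It does not supply a group comparison or the promised statistics.

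Third, a reader might infer that these doublings stay inside the normal range, or that a doubling usually goes ungraded. Neither can be said. The laboratory limits are in the MOP, and the documents give no distribution of baseline ALT. If the upper limits were 40 and 54.8 U/L (an assumption: the top of Grade 1 divided by 2.5, 100/2.5 and 137/2.5), doublings inside the range would stop at baselines of 20 and 27. A rise to 42 or 58 would then be out of range and appear in Table 29, while still counted as *None* in Table 33.

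Fourth, the animal evidence should not be overstated. The two-fold figure comes from the highest dose in one rat study without histopathological confirmation. Protocol 2.3.1 also reports no clinically significant liver-enzyme change at any dose in the single-dose trial.

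**Conclusion.** The point holds as an undeclared gap between promise and output. Numeric summaries of value and change are promised for laboratory, ECG and vital-sign data; none has a specified output.

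The exact size for ALT is that a doubling from a baseline of up to 21 U/L (women) or 29 U/L (men) is ungraded. For QTcF, it is a rise below 30 msec ending at or below 450 msec (men) or 470 msec (women). How many participants fall there is unknown. The conclusion assumes that the final tables follow the shells.

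A reader might go further and infer that the report will claim no liver or ECG signal when the data show one. That is conjecture, because the listings carry the individual changes. What can be said is that, run as shelled, the plan compares no group-level shift below the grading limits with placebo. This should be corrected, and doing so is cheap.

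**What to change.** Add one table each for chemistry, hematology, coagulation, supine vital signs and ECG intervals. Each should give n, mean, SD, median, minimum and maximum of the value and of the change from baseline, by time point and treatment group, as protocol 9.3.6 states. Include the collected but ungraded parameters named above. Refer to the new tables in SAP 9.6, 9.7 and 9.9.1.

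SAP 15 allows an addendum before final data lock and no amendment after it; the documents do not say whether lock has occurred. If it has, produce the tables for the clinical study report and describe the difference from the SAP there.

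A ratio to baseline for the liver tests would be useful but is optional; the protocol does not require it. The cost is some SAP or report wording and a few standard tables from data already collected.

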## 9.7. Vital Signs and Physical Evaluations

Unscheduled supine or orthostatic VS measurements will be included in listings but will be excluded from tabular and graphical summaries by time point, except when calculating the maximum severity post baseline. If VS measurements are repeated due to technical errors, the initial measurements made in error will not be used for analysis but will be listed. The following rules will be used to determine which supine VS measurement to use for analyses if repeat measurements occur:

1. If the first replicate is normal, then it will be used for analysis.
2. If the first and second replicates are both abnormal, then the replicate with the higher severity will be used for analysis.
3. If the first replicate is abnormal, the second replicate is normal, and the third replicate was not performed, then the first replicate will be used in the analysis.

4. If the first replicate is abnormal, the second replicate is normal, and the third replicate is normal, then the second replicate will be used in the analysis.
5. If the first replicate is abnormal, the second replicate is normal, and the third replicate is abnormal, then the abnormal replicate with the higher severity will be used for analysis.

Any supine VS assessment at Screening or Check-in (Day -1) with values in the Grade 1 range but deemed acceptable for enrollment per [Section 4.3.1](#), inclusion criterion #4, will be presented in listings but will only be reported as a TEAE if severity worsens. VS assessments that have grading criteria for both decreases (result lower than normal range) and increases (result higher than normal range) will be summarized separately by direction.

The sort order for VS will be as follows: Oral Temperature, SBP, DPB, Pulse, and Respiratory Rate.

Supine VS results will be summarized in tables:

- Number and percentage of participants with mild, moderate, severe, or life-threatening VS results both low (decrease) and high (increase) by parameter, time point, dose (morning or evening), and treatment group ([Table 37](#)).

Following supine measurements, orthostatic measurements of blood pressure and heart rate (pulse) were taken at 1 min ( $\pm 15$ s) and 3 min ( $\pm 15$ s) after standing. These measurements were evaluated relative to the supine measurements that were taken before standing up. The criteria for an abnormal VS orthostatic response include the following:

- Orthostatic hypotension, defined as an SBP decrease of at least 20 mm/Hg **and/or** a DBP decrease of at least 10 mm/Hg from supine baseline,
- **And** an increase in orthostatic pulse defined as an increase of at least 30 beats/min above supine baseline or any time there was tachycardia with a pulse above 120 beats/min.

Abnormal VS orthostatic response meeting these criteria will be summarized as a TEAE. Orthostatic BP and HR are not included in VS tables. If orthostatic measurements were repeated, then supine measurements were repeated first.

All supine and orthostatic VS measurements will be presented in [Listing 17](#).

Abnormal physical exams will be submitted and counted as an AE. A listing of abnormal physical exams will be presented in [Listing 18](#).

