- **Vital Signs (VS) inclusive of orthostatic blood pressure and heart rate:** Include body temperature (oral), BP (resting more than 5 min), RR, and HR. Heart rate and BP will be measured at rest with the participant supine for at least 5 minutes. VS will be measured twice daily within 30 min before and 2h (\pm 10 min) after each dose on Days 1 to 7, once daily in the morning on Days 8 and 9, or at ET. Abnormal VS may also be measured at unscheduled visits as needed for follow up of AEs. Repeat measurements with the participant supine may be allowed if the first measurement is abnormal (See [Section 8.3.3](#)).¹

Note 1: Orthostatic blood pressure and heart rate will be obtained and recorded after the supine VS, while the participant is in the standing position with measurements taken at 1 minute \pm 15 seconds and 3 minutes \pm 15 seconds after standing.

- **ECG:** A standard 12-lead ECG will be recorded, within 30 min before the morning dose on Day 4, on Day 8 before the 12h blood (plasma) PK collection after the evening dose on Day 7, or ET. Additional ECGs may be recorded as needed for the evaluation of TEAEs. The participant should be in a supine position and should have an approximate 10-minute rest period prior to ECG recordings.

A physician (PI or coinvestigator) or clinician who is licensed to make diagnoses (listed on Form FDA 1572) will evaluate the ECG for any abnormalities in ECG intervals including QT/QTcF, and any morphologic abnormalities for clinical significance. If a question regarding ECG interpretation arises, the study investigators will have the ECG reviewed by a cardiologist.

8.3.2 **Laboratory Evaluations**

- **Clinical Laboratory Assessments:**

- Blood for HEM, CHEM, and COAG will be collected before the morning dose on Days 2, 4, and 6, and on Day 8, or ET for the evaluation of the same tests listed in [Section 8.1.2](#). Clinical lab tests may also be performed at unscheduled visits as needed for follow up of AEs. Participants must be fasting at least for 4 h before any blood draw for clinical laboratory assessments.
- UA will be collected before the morning dose on Day 4 and on Day 8, or ET (See [Section 8.1.2](#))

8.3.3 **Procedures to be Followed in the Event of Abnormal Clinical Laboratory Test Values or Abnormal Clinical Findings During Conduct of the Trial**

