All abnormal clinical findings or abnormal clinical laboratory test values post treatment will be considered AEs and followed up as AEs. If a physiologic parameter, e.g., VS or clinical laboratory value, is outside of the protocol-specified range, then the measurement may be repeated if, in the judgment of the participating site PI or appropriate licensed sub-investigator or clinician, the

abnormality is the result of an acute, short-term, rapidly reversible condition (e.g., stress, anxiety or “white coat syndrome”) or other source of error (e.g., a technical problem with the measurement caused by malfunctioning, or an inappropriate measuring device (i.e., inappropriate-sized BP cuff), or error in collecting or processing the clinical laboratory sample. If the repeat measure is within normal range, the most accurate value will be used. Any abnormal parameters will be recorded in the medical record.

Once dosed with study product, lab results that are above the upper limit of normal or below the lower limit of normal for the baseline reference ranges but are less than Grade 1 in the toxicity table, will not be graded and reported as outside the normal range. Lab results that were acceptable for enrollment within the Grade 1 toxicity range of the FDA toxicity tables will be graded as AEs if the on-study values are higher or lower than the baseline value and fall within the range of AEs with “increased” or “decreased” values.

Procedure followed for Abnormal Supine Vital Signs (Post Dosing On Days 1 through 9, or ET):

- Any time after the start of the oral dose administration, any abnormalities in supine VS that occur either due to technical or procedural error or the result of an acute, short-term condition as assessed by the PI (e.g., stress, anxiety, white coat syndrome) may be repeated twice more at rest, while the participant is in the supine position and at least 5 min of each other.
- If the second VS is abnormal, then the highest severity grade between the first and second measurements will be used for assessment of TEAE per [Appendix A](#).
- If the second VS is normal, then a third repeat is to be taken at least 5 min of the previous measurement.
- If the third value is abnormal, the highest grade of severity between the first and third measurements will be used for assessment of TEAE per [Appendix A](#).

8.3.4 Blood sampling for Plasma SLV213 Assay during the In-patient Period and Serum for Future Research

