**Table 7: Vital Sign Grading Scale**

Supine (at rest)				
Parameter	Grade 1/Mild	Grade 2/Moderate	Grade 3/Severe	Grade 4/ Potentially Life-Threatening
Fever  (°C) (°F)	38.0 – 38.4 100.4 – 101.1	38.5 – 38.9 101.2 – 102.1	39.0 – 40 102.1 – 104	> 40 > 104
Tachycardia – bpm	101 – 115	116-130	> 130	ER visit or hospitalization for arrhythmia
Bradycardia  – bpm, when baseline HR 60-100 bpm	50 – 54	45 – 49	< 45	ER visit or hospitalization for arrhythmia
Sinus Bradycardia  – bpm, when baseline HR <60 bpm	45 – 49	40 – 44	<40	Life-threatening consequences, urgent intervention indicated
Hypertension (diastolic) – mmHg	91 – 95	96 – 100	> 100	ER visit or hospitalization for malignant hypertension
Hypertension (systolic) – mmHg	141 – 150	151 – 155	> 155	ER visit or hospitalization for malignant hypertension
Hypotension (systolic) – mmHg	85 – 89	80 – 84	< 80	ER visit or hospitalization for hypotensive shock
Respiratory Rate – BPM	17 – 20	21 – 25	> 25	Intubation

 Oral temperature; no recent hot or cold beverages or smoking.

 Use clinical judgement when characterizing bradycardia among some healthy participant populations (e.g., conditioned athletes).

*Note: Isolated/individual abnormalities of VS would not be considered toward halting criteria. Abnormalities of VS will be described as “increased X” or “decreased X” (X = HR, BP, RR, temperature) if asymptomatic, transient, and not associated with a systemic or organ-specific disorder and coded by MedDRA within the System Organ Class (SOC) “Investigations.” These abnormalities will be graded per criteria in this table, but not considered in determining whether study stopping criteria have been met. On the other hand, abnormalities of VS that are either secondary to systemic or organ-specific clinical syndrome or primary disorders will be coded in the appropriate SOC (e.g., “cardiac disorders”, “respiratory disorders”, “immunological disorders”, etc.). These abnormalities will be considered in determining whether stopping criteria have been met.*

**12.4.1 Individual Laboratory Measurements and Abnormal Laboratory Values****Table 8: Laboratory Adverse Event Grading Scale**

Parameter	Grade 1/Mild	Grade 2/Moderate	Grade 3/Severe	Grade 4/ Potentially Life- Threatening
Chemistry				
Sodium increase – mmol/L	144 – 145	146 – 147	148 – 150	> 150
Sodium decrease – mmol/L	132 – 134	130 – 131	125 – 129	< 125

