## 16.2.9 Vital Signs and Physical Exam Findings

### Listing 17: 16.2.9.1: Vital Signs

**[Implementation Note:** This includes all vital sign assessments, scheduled and unscheduled. This listing is not color-coded, but the severity should be included in parentheses after the result for abnormal supine results, e.g., 141 (Mild).

Listing will be sorted by Treatment Group, Participant ID, Study Day, and Planned Time Point.]

Treatment Group	Participant ID	Study Day (Dose)	Planned Time Point	Actual Time Point	Temperature (°C)	Systolic Blood Pressure (mmHg)			Diastolic Blood Pressure (mmHg)			Pulse (beats/min)			Respiratory Rate (breaths/min)
						Supine	Standing (1 min)	Standing (3 min)	Supine	Standing (1 min)	Standing (3 min)	Supine	Standing (1 min)	Standing (3 min)	
		Day 1 (Morning)	-30M	-32M	36 (None)	120 (None)	116	112	60 (None)	68	57	60 (None)	68	70	12 (None)
		Day 1 (Morning)	2H	2H 5M											
		...	...	...											
		Day 8	-												
		Day 9	-												

Note: Systolic blood pressure, diastolic blood pressure, and pulse standing measurements that meet the criteria for an abnormal orthostatic response are graded according to Adverse Event Grading Scale and are included in [Listing 12: 16.2.7.3 Treatment Emergent Adverse Events](#).

Time point refers to the amount of time before or after the associated dose that supine vital signs were collected. Standing vital signs were collected 1 min ( $\pm 15$  s) and 3 min ( $\pm 15$  s) after supine vital signs were collected.

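### Read literally, SAP 9.7 counts a measured orthostatic response as a TEAE only when pressure falls and pulse rises together, and no table shows standing blood pressure or pulse

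*SAP*

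**What the plan says.** SAP 9.7 compares standing pressure and pulse, 1 and 3 minutes after standing, with the supine values taken just before. It gives two bullets. The first is orthostatic hypotension: a systolic fall of at least 20 mmHg and/or a diastolic fall of at least 10 mmHg. The second opens with a bold And and requires "an increase in orthostatic pulse defined as an increase of at least 30 beats/min above supine baseline or any time there was tachycardia", the tachycardia being a pulse above 120 beats/min. The consequence follows: "Abnormal VS orthostatic response meeting these criteria will be summarized as a TEAE. Orthostatic BP and HR are not included in VS tables".

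The Listing 17 footnote uses the same gate: "pulse standing measurements that meet the criteria for an abnormal orthostatic response are graded according to Adverse Event Grading Scale", and it sends those readings to Listing 12. Table 7 grades supine vital signs at rest only, and Table 37, the one vital-signs results table, is supine.

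The protocol reads differently:

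- Section 8.3.1 lists "Vital Signs (VS) inclusive of orthostatic blood pressure and heart rate" as a single assessment.
- Section 8.3.3 says: "All abnormal clinical findings or abnormal clinical laboratory test values post treatment will be considered AEs and followed up as AEs".
- Section 9.3.6 says that "baseline, post dose, and changes from baseline to post dose laboratory, VS, and ECG data will be summarized".

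No pulse condition for an orthostatic AE appears anywhere in the protocol. The changes declared in SAP 15 concern only the stop after Cohort 1.

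**The concern.** Type, incidence and severity of TEAEs is the primary safety endpoint. The protocol's background sections single out one clinically significant episode from the single-dose study, and it was orthostatic hypotension. The amendment history for version 3.0 records that orthostatic evaluation was added to the medical history and vital signs after FDA non-hold questions. These readings were therefore collected for a purpose.

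Under the literal rule, a response that meets the SAP's own definition of orthostatic hypotension is not summarised as a TEAE unless the pulse also qualifies. With no table of standing values, a reader cannot compare SLV213 with placebo except by subtracting and counting by hand in Listing 17. That listing attaches severity only to supine results and shows standing values rather than differences. Whether a single-limb response is counted then depends on an undeclared pulse condition or on individual reporting.

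**Working it through.** No sample-size or power figure is involved. The check has three parts.

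**1. The rule.** With all changes taken from the supine reading, the literal text is:

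TEAE = (SBP fall ≥ 20 or DBP fall ≥ 10) AND (pulse rise ≥ 30 or standing pulse > 120)

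The first two rows below are the mock readings in the Listing 17 shell. The rest are assumed values chosen to exercise each limb.

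| Case | Supine (BP, pulse) | Standing (BP, pulse) | Fall SBP/DBP | Pulse change | BP limb | Pulse limb | AND | OR |
|---|---|---|---|---|---|---|---|---|
| Listing 17 mock, 1 min | 120/60, 60 | 116/68, 68 | 4/−8 | +8 | no | no | no | no |
| Listing 17 mock, 3 min | 120/60, 60 | 112/57, 70 | 8/3 | +10 | no | no | no | no |
| Pressure only | 120/80, 70 | 90/65, 85 | 30/15 | +15 | yes | no | **no** | yes |
| Pulse rise only | 120/80, 70 | 118/80, 105 | 2/0 | +35 | no | yes | **no** | yes |
| Pulse above 120 only | 120/80, 95 | 118/80, 122 | 2/0 | +27 | no | yes | **no** | yes |
| Both | 120/80, 70 | 95/68, 102 | 25/12 | +32 | yes | yes | **yes** | yes |

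Of the three abnormal patterns (pressure only, pulse only, both), the literal rule passes one. Near the limits, a systolic fall of 40 mmHg with a 29-beat rise to 100 fails, because 29 < 30 and 100 is not above 120. A 40-beat rise to 110 with falls of 19/9 mmHg also fails, because 19 < 20 and 9 < 10.

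**2. The volume of data.** Protocol 8.3.1 schedules vital signs before and 2 h after each dose on Days 1 to 7, and once on each of Days 8 and 9.

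- Sessions: 14 doses × 2 + 2 = 30.
- Standing readings: 30 × 2 (1 and 3 min) = 60.
- Post baseline, leaving out the Day 1 pre-morning session: 29 sessions and 29 × 2 = 58 readings.
- Values: 58 × 3 (SBP, DBP, pulse) = 174 per completer.

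**3. The displays.** Among Tables 1–39, vital-sign results appear only in Table 37, which is supine, and in the Grade 3 vital-signs row of Table 14, which has only the supine grades of Table 7 to draw on. None of Figures 1–10 shows vital signs. Among Listings 1–26, standing values appear only in Listing 17.

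**Consistency within the SAP.** Section 9 repeats the commitment to summarise baseline, post-dose and change-from-baseline vital signs. Section 9.7 says "Unscheduled supine or orthostatic VS measurements will be included in listings but will be excluded from tabular and graphical summaries by time point". Excluding only unscheduled readings suggests that scheduled orthostatic ones are tabulated, but the same section later rules them out and no shell exists.

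**The case against.** **The conjunction is not settled.** The lead-in says the criteria include the two bullets, and a pulse above 120 at any time could be a stand-alone trigger. Under an OR reading, all four abnormal cases above become TEAEs. This stands as an ambiguity. The bold and/or inside the first bullet, set against the bold And opening the second, favours the conjunctive reading, but the authors need to say which they mean. Under either reading no table shows standing values.

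**Reporting routes remain.** Protocol 8.3.1 makes orthostatic symptoms TEAEs, Protocol 8.3.3 makes abnormal findings AEs, and SAP 4.5.1 sends abnormal assessments to an AE form. SAP 9.7 does not say that a reported single-limb event is removed. This is right and it narrows the gap to measured responses, typically asymptomatic, that nobody reports. It does not close the gap, because the SAP and its listing footnote state a different rule for measured values and no table offers a check.

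**Protocol 9.3.6 is weak support.** Change from pre-dose baseline is not the supine-to-standing contrast within a session, and the supine readings have no change-from-baseline table either. This stands, as does the point that the sentence on unscheduled readings implies a table without promising one. The core finding does not depend on either.

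**Importance.** The earlier episode was in one participant at 200 mg. It did not recur in that participant and was not seen at 400 or 800 mg, and the review committee found no dose-limiting toxicity. This trial stopped after moderate allergic reactions, and the report is abbreviated. These facts limit the stakes. Even so, at the same sample size supine vital signs get a full by-time-point table.

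**Conclusion.** The concern holds and should be fixed. On its literal wording, SAP 9.7 leaves out of the TEAE summary a response that meets its own definition of orthostatic hypotension, unless the pulse limb is also met or the investigator reports the event. The pulse condition is absent from the protocol and is not declared in SAP 15. Whichever way the conjunction is read, 58 post-baseline standing readings per completer reach no table or figure.

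The finding assumes the conjunctive reading for the TEAE count and no separate AE report for the single-limb response. No loss rate can be given, because the documents contain no distribution of standing changes. Which orthostatic definition is clinically right is not judged here.

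**What to change.** Use the addendum route in SAP 15, before final data lock:

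1. Reconcile SAP 9.7 and the Listing 17 footnote with Protocol 8.3.1, 8.3.3 and 9.3.6. State whether both limbs are needed for TEAE status and whether a pulse above 120 qualifies alone. The clinical definition of an orthostatic AE stays with the sponsor.
2. If a pulse condition is kept, list it in SAP 15 among the changes from Protocol v4.0.
3. Add one Safety Population table by treatment group. Its rows are baseline, each scheduled time point (pre- and post-dose, morning and evening, Days 1–7; then Days 8 and 9) and any time post baseline. Each row gives n/N and % of participants meeting (a) the SAP's pressure limits, (b) the SAP's pulse limits and (c) both. A participant counts once per cell if either the 1-minute or the 3-minute reading qualifies.

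The cost is SAP wording and one descriptive table from data already collected. By scheduled time point it has 30 × 3 criteria × 2 arms = 180 cells, plus the any-time row, and it is no larger than Table 37. With 58 post-baseline readings per completer, the any-time row may be high in both arms, so it must be read against the baseline and by-time-point rows. The table does not itself change TEAE incidence, and it does not supply descriptive change-from-baseline statistics for vital signs.
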